Older obese adults suffer disproportionately from walking mobility limitations. Sedentary, obese older adults are at an increased risk for having or developing difficulties with mobility. These individuals are often excluded from studies due to their advanced mobility limitations. A number of studies have compared the effects of weight loss alone, exercise alone, or weight loss in combination with exercise on functional performance in older adults, but none of the studies have specifically targeted subjects who use walking assistive devices. The purpose of this study is to test the effects of a 3 month multi-modal balance intervention (MMBI) with a nutrition program with optional retention till 24 months on fitness, functional performance, mobility, and muscle mass. The results of this study will lead to new and more effective interventions that could reduce disability, fall risk, injury-related hospitalization and death in older Veterans.

ID: VIEW4E02805CF7000
Name: v2_Lay Summary

Justification, Objective, & Research Design

If you uploaded a separate research protocol document in the 'Research Protocol' page, cite the applicable section and page numbers from that document in the answer boxes below.

- 1 *** Describe the purpose, specific aims, or objectives of this research. State the hypothesis to be tested:**
 Specific aim 1: Examine the effects nutrition + multimodal balance intervention (MMBI) on mobility and functional performance in the following outcomes:
 a. 6 minute walk (primary outcome)
 b. Other physical performance outcomes: 6MW with economy of gait, gait rite, four square step test, 8 foot up and go, short physical performance battery, grip strength, lower extremity strength
 Specific aim 2: Examine the relationship between muscle mass, strength, and functional performance using DXA and CT scans to quantify body composition.
 Specific aim 3: Examine the impact of the intervention on patient reported measures of function and disability using the Late Life Function and Disability Instrument (LLFDI).
- 2 *** Discuss the research design including but not limited to such issues as: probability of group assignment, potential for subject to be randomized to placebo group, use of control subjects, etc.:**
 All subjects will now receive MMBI and nutrition (combined intervention). Weight loss will be a covariate in the analyses.
- 3 *** Describe the relevant prior experience and gaps in current knowledge. Describe any relevant preliminary data:**

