Several prominent studies have examined the role of exercise as an intervention to prevent or retard the onset of mobility disability. In the Lifestyle Interventions and Independence for Elders Pilot Study (LIFE-P), 19,34-36 a total of 424 sedentary persons, ages 70-89 years at risk for disability, were randomized to a moderate-intensity physical activity(PA) intervention or a successful aging (SA) health education intervention and were followed for an average of 1.2 years. It is important to note that subjects who used a cane or other walking assistive device to complete the 400 meter walk test were excluded from the study. The baseline SPPB scores of 7.5 were similar in both groups. With intervention, PA had higher SPPB scores at 6 and 12 months versus SA of $8.7 + 0.1$ versus $8.0 + 0.1$, and $8.5 + 0.2$ versus $7.9 + 0.2$, respectively ($p < .001$). The 400-meter walking speed was essentially unchanged in PA compared to a slight decline in SA. The PA group had a lower incidence of major mobility disability (inability to complete a 400-meter walk). In the LIFE-P obesity blunted the beneficial response to the physical activity intervention such that the non-obese individuals had a 5 times greater improvement in long-distance walking speed than obese individuals in the intervention group. 36 Our subjects will differ substantially from those in LIFE-P due to our selection criteria for obesity and requirement that subjects use walking assistive devices. In LIFE-P, the average BMI was 30.2. In addition, 42% were obese with $BMI > 30$. 31 Unlike the proposed study, there was no nutrition component in LIFE-P. Lifestyle Interventions and Independence for Elders (LIFE) Study was a randomized control trial of lifestyle interventions designed to preserve the ability to walk in older adults. The study compared a moderate-intensity physical activity program to a successful aging health education program in 1,600 sedentary older adults who are followed for an average of 2.7 years. 18,37 The primary aim was to assess the long-term effects of the interventions on the primary outcome of major mobility disability, defined as inability to walk 400 m. The study demonstrated that the physical activity intervention decreased subsequent major mobility disability by 18%>.38 The LIFE study excluded those who used a walker to complete the 400 m walk and/or those who were unable to complete the 400 m walk without sitting down or with the help of another person.

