2 * Provide the plan for data analysis. Include in the description the types of comparisons that are planned (e.g., comparison of means, comparison of proportions, regressions, analysis of variance, etc.), which is the primary comparison/analysis, and how the analyses proposed will relate to the primary purposes of the study:

All comparisons of primary and secondary outcomes will be performed in accordance with intention-to-treat principles. As with all clinical trials, it is anticipated that there may be missing data elements. Multiple imputation will be used to account for missing values. Our first analyses will be exploratory designed to identify extreme values. Extreme values will be checked to make sure they are not the result of data entry errors. Statistical significant will be a two-sided alpha of 0.05.

Specific aim 1. Our study will compare the effects of MMBI+nutrition on mobility and functional performance in older obese Veterans with walking impairment requiring a walking assistive device. We will use repeated measures ANOVA to model the time-course of our outcome measures. We will use AICC (a modification of Akaike's Information Criterion) to choose between three covariance structures that can account for the serial auto-correlation of our subject's data.

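### A significant SPPB time effect in this one-group design does not show an effect of MMBI + nutrition, because the plan's own LIFE-P figures imply that health-education controls rose by 0.4 to 0.5 points

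*Combined protocol and SAP*

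**What the plan says.** - **Design** (Justification, Objective, & Research Design, item 2): "All subjects will now receive MMBI and nutrition (combined intervention). Weight loss will be a covariate in the analyses". There is no concurrent comparison group.
- **Outcome** (same section, item 1): the 6-minute walk is primary. SPPB is one of the other performance outcomes of Specific aim 1, in the list "four square step test, 8 foot up and go, short physical performance battery, grip strength, lower extremity strength". The aim is worded as examining the effects of the intervention.
- **Analysis** (Sample Size and Data Analysis, item 2): "We will use repeated measures ANOVA to model the time-course of our outcome measures", and "Statistical significant will be a two-sided alpha of 0.05". No control, external reference, minimum change or allowance for background gain is given for SPPB.
- **Background evidence** (Supporting Literature, item 1, on LIFE-P): "The baseline SPPB scores of 7.5 were similar in both groups". The successful-aging (SA) health-education group is then reported at 8.0 at 6 months and 7.9 at 12 months, and the physical-activity group at 8.7 and 8.5.
- **Timing** (Study Procedures, item 1): the intervention lasts 3 months. Assessments at 6, 12 and 24 months apply to those who take the optional extension.

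**The concern.** In a one-group repeated measures ANOVA the testable effect is time, and its null hypothesis is no mean change. That answers whether SPPB moved. Aim 1 asks what the intervention did. The two questions coincide only if SPPB would have stayed flat without the intervention, and the plan cites figures suggesting otherwise: a group given health education ended above its baseline at both follow-ups.

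If a significant time effect is then reported as a benefit of MMBI + nutrition, the 5% error rate attached to it does not cover that statement. A gain no larger than that of the LIFE-P controls could be presented as a treatment effect, in a plan that foresees wide use of the programme at other VA sites. Entering weight loss as a covariate does not supply the missing comparison.

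**Working it through.** **Inputs from the documents**
- LIFE-P SPPB (Supporting Literature): baseline 7.5 in both groups; controls 8.0 and 7.9, activity group 8.7 and 8.5, at 6 and 12 months.
- GeroFit pilot, 16 obese Veterans (Justification, item 3): SPPB 8.5 (SD 1.7) at baseline and 9.56 (SD 2.1) at 3 months.
- Completers (Sample Size, item 1): 60 enrolled with attrition up to 25%, and 60 × 0.75 = 45, which reproduces the plan's figure. The plan states no power or error rate for SPPB, so there is no SPPB figure to reproduce.
- Two-sided alpha 0.05, hence 2.5% in the improving direction.

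**Assumption.** The SD of SPPB change is not given, so a pre-post correlation r has to be assumed. The working range is 0.5 to 0.7, with 0.3 and 0.9 as outer values.

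**Step 1, implied gains**
- Controls: 8.0 − 7.5 = 0.5 (6 months); 7.9 − 7.5 = 0.4 (12 months).
- Activity group: 8.7 − 7.5 = 1.2; 8.5 − 7.5 = 1.0.
- Control gain as a share of the activity-group gain: 0.5/1.2 = 42%; 0.4/1.0 = 40%.

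**Step 2, SD of change** = √(1.7² + 2.1² − 2·r·1.7·2.1) = √(7.30 − 7.14r)
- r = 0.3: 2.27
- r = 0.5: 1.93
- r = 0.7: 1.52
- r = 0.9: 0.93

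**Step 3, probability of a significant improvement when the only true change is background gain d.** With two time points the time effect is equivalent to a one-sample t test of change. Its noncentrality is d·√n / SD, and the upper critical value is 2.015 for n = 45 and 2.080 for n = 22. Example: d = 0.5, n = 45, r = 0.5 gives 0.5 × 6.708 / 1.931 = 1.74, and the upper-tail probability is 40%.

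| Scenario | d | n | r = 0.5 | r = 0.7 |
|---|---|---|---|---|
| 12-month control gain | 0.4 | 45 | 27% | 41% |
| 6-month control gain | 0.5 | 45 | 40% | 58% |
| Half the gain by 3 months (assumption) | 0.20 | 45 | 10% | 14% |
| Half the gain by 3 months (assumption) | 0.25 | 45 | 13% | 19% |
| About half continue to 6/12 months (assumption) | 0.4 | 22 | 15% | 22% |
| About half continue to 6/12 months (assumption) | 0.5 | 22 | 21% | 31% |

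With n = 45 and gains of 0.4 / 0.5, the outer correlations give 21% / 30% at r = 0.3 and 80% / 94% at r = 0.9.

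**Step 4, more than two time points.** An omnibus F test over baseline, 6 and 12 months, with means 0, 0.5 and 0.4 and n = 45, is significant in 54% of trials at an SD of change of 1.5 and 33% at 2.0. The nominal rate for that test is 5%. The result does not depend on reducing the model to a t test.

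**The case against.** **Timing.** The LIFE-P values are at 6 and 12 months, the core intervention here lasts 3, and the plan does not say how many subjects will continue. Pairing the full 0.4-0.5 gain with 45 completers is therefore the least favourable combination for the plan. This stands, and it is why the 10-19% and 15-31% scenarios belong beside the 27-58%. They remain well above 2.5%.

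**Quality of the reference.** The gain is a subtraction of reported means. The plan does not say whether the follow-up values are model-adjusted or come from the same people as the baseline, and the values attached with plus signs are unlabelled. The plan itself says its subjects will differ substantially from those in LIFE-P. This also stands. It rules out treating 0.5 as a known constant, but it does not make zero a better-supported reference.

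**No written success rule.** The plan says it will model the time course and gives no SPPB criterion, and the planned model also has imputation, a selected covariance structure and a covariate. A reader might infer that the plan declares success from an SPPB p-value, or that the ANOVA's own error rate is wrong. The documents support neither: the 5% rate for the hypothesis of no change is intact, and the difficulty is attribution.

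**Selective evidence.** A reader might carry the argument over to the 6-minute walk. The same LIFE-P account reports a slight decline in control walking speed, so it shows no general upward drift in mobility and gives no support for that extension.

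**Conclusion.** The point holds for SPPB, a secondary outcome. With every subject treated, a significant time effect shows change from baseline and does not show an effect of MMBI + nutrition.

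A background gain of the size the plan's own figures imply would by itself be significant in about 27-58% of trials. That range assumes n = 45, the GeroFit SDs, r = 0.5 to 0.7, and LIFE-P drift carried over in full. Under the milder assumptions it is about 10-31%. The true 3-month drift in this population is unknown, so these are illustrations of size and not estimates of this trial's error rate.

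Two stronger statements go too far. One is that untreated people gain 0.4 to 0.5 points: the LIFE-P comparison group received health education. The other is that false claims would be near-certain: the 94% figure needs r = 0.9 together with the full 6-month gain and 45 subjects.

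**What to change.** Add to the Specific aim 1 analysis in Sample Size and Data Analysis, item 2:

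- SPPB will be reported as uncontrolled change from baseline with its 95% confidence interval, shown beside the LIFE-P control gain of 0.4 to 0.5 points as context.
- A p-value below 0.05 for time will not be used to claim an intervention effect on SPPB.
- The limits of the reference will be stated: values at 6 and 12 months rather than 3; ages 70-89; 42% obese; users of a cane or other walking device on the 400 m walk excluded; comparison group given health education.

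The 0.5 points should not become a fixed pass mark. The value is uncertain and comes from a different population and time point. A rule requiring the lower confidence limit to exceed it could also miss a real effect. At the GeroFit gain of 9.56 − 8.5 = 1.06 with 45 completers, the power of that rule is 37% at r = 0.3, 48% at r = 0.5 and 68% at r = 0.7.

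The cost is a few sentences and a weaker SPPB conclusion. No new data, visits or subjects are needed.

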5.1 If Yes, what procedures are in place to assure safety?

ID: VIEW4E09460F5EC00
 Name: v2_Surveys/Questionnaires

Sample Collection/Analysis

You indicated on the "Type of Research" page that your study involves a sample (specimen) collection and/or analysis.

1 * What type of samples will be involved in this study? (Check all that apply)

Prospective (will be collected)
 Existing (previously collected at the time of initial IRB submission)

2 * Will genetic analysis/testing be done on any of the samples?

Yes No

3 * Will this study involve banking of samples (storing for future research use)?

Yes No

4 * What is the purpose of the sample collection and/or analysis?

At screening - for eligibility purposes and to characterize the health status of this subject population. At baseline, 6 months, and 12 months to assess for inflammation and stored samples for a biorepository for future use.

5 * Is there the possibility that cell lines will be developed with any of the samples?

Yes No

6 * Will the samples be released to anyone not listed as an investigator on the protocol?

Yes No

6.1 If Yes, give name(s) and affiliation(s):

7 * Will the sample material be sold or given to any third parties?

Yes No

7.1 If Yes, give name(s) and address(es):

ID: VIEWIE0Efa4B80000
Name: v2_Sample Collection/Analysis

Prospective Samples

You indicated that the study involves collection of prospective samples (specimens).

1 * What type of sample will be collected? (Check all that apply)

- Blood
- Bone Marrow Aspirate/Biopsy
- Cerebrospinal Fluid
- Saliva
- Skin
- Sputum
- Stool
- Tissue
- Tumor
- Urine
- Other

1.1 If Other, specify:

2 For blood draws, specify the amount drawn, in teaspoons, at each visit and across the course of the subject's entire participation time:

Approximately 60 cc at screening
 Approximately 40 cc at 3 months
 Approximately 30 cc at 12 months
 Total = approximately 130 cc

3 * What type of samples will be collected? (Check all that apply)

- Samples obtained specifically for research purposes-obtained via a separate collection procedure done solely for the purposes of the study
- Samples obtained specifically for research purposes-additional taken during a clinical procedure
- Leftover samples that were obtained for clinical purposes (no additional research procedures required)
- Commercial (for profit) samples
- Other

3.1 If Other, specify:

4 * How are these samples labeled? For example, do they contain name, initials, dates, Social Security number, medical record number, or other unique code?

Samples are stored with a unique code and the date the sample was obtained.

5 * Will sample(s) be made available to the research subject (or his/her medical doctor) for other testing?

Yes No

6 * If a participant withdraws from the study, will that participant have the option to get the remaining portion of their sample(s) back?

Yes No

7 * If the participant withdraws, explain how their sample(s) will be handled (For example, will sample(s) be destroyed, anonymized, etc.):

Samples will be banked at the GRECC and the Division of Gerontology and Geriatric Medicine at the Baltimore VAMC indefinitely unless the subject requests any remaining samples be destroyed.

8 * Will the samples be destroyed after the study is over?

Yes No

8.1 If No, describe how the samples will be stored, where they will be stored, and for how long.

Samples will be banked at the GRECC and the Division of Gerontology and Geriatric Medicine at the Baltimore VAMC indefinitely unless the subject requests any remaining samples be destroyed.

Sample Banking

You indicated that the study involves banking of samples (storing for future research use).

- 1 * Where will the sample(s) be banked? (If this study involves the VA, please state the name of the registry/repository and the CICERO protocol number it was approved under.)
Metabolic Core Lab, UMB-Pepper Center, Baltimore VAMC
- 2 * Does the banking institution have an approved policy for the distribution of samples?
 Yes No
- 3 How long will the sample(s) be kept?
Samples in biorepository will be retained indefinitely.
- 4 * Will sample(s) be made available to the research subject (or his/her medical doctor) for other testing?
 Yes No
- 5 * If a participant withdraws from the study, will that participant have the option to get the remaining portion of their sample(s) back?
 Yes No
- 6 * If the participant withdraws, explain how their sample(s) will be handled (For example, will sample(s) be destroyed, anonymized, etc.):
Samples will be retained unless a participant requests they be destroyed.
- 7 * If the participant withdraws, explain how the data obtained from their sample(s) will be handled (e.g., will it be deleted)?
(Please note that data for FDA regulated research cannot be deleted):
Results of all testing on samples will be retained in the study database

ID: VIEW4E0E7E82B5800
Name: v2_Sample Banking

Data Collection/Record Review

You indicated on the "Type of Research" page that your study involves data collection or record review (i.e., chart review, not self-report).

1 * What type of data will be collected/analyzed in this study? (Check all that apply)

Retrospective/Secondary Analysis (data has already been collected at the time of initial IRB submission)
 Prospective (data is not yet in existence and/or collected)

2 * Will this study involve adding data to a registry or database for future use?

Yes No

3 * Will the data be released to anyone not listed as an investigator on the protocol?

Yes No

3.1 If Yes, give name(s) & affiliation(s):

ID: VIEW4E0E25ABC400
Name: v2_Data Collection / Record
Review

Prospective Data

You indicated that the study involves the collection of prospective data.

1 * Where is the data being collected from? (Check all that apply)

- Medical records
- Medical images
- Commercial (for profit) entity
- Publicly available records
- Schools
- Other

1.1 If Other, please specify:

Physical exams and research testing

2 * What data fields will you have access to/collect for the study? For example, name, initials, date of birth, Social Security number, income, demographic information, family units, housing, etc.

Enrollment into CPRS requires full name, date of birth, social security number, address, and gender. On our general information sheet, we collect income, ethnicity, race, marital status, work status, health insurance, and previous occupation among others. In addition we will measure variables related to health status, physical functional, strength, fitness, body composition, quality of life, fatigue, disability, balance, gait, and fall risk. We will be sharing data with HP-00060757 in order compare different participant populations doing similar testing and measurements.

You can also upload a copy of the data fields/variables to be collected for the study:

Name	Created	Modified Date
------	---------	---------------

There are no items to display

ID: VIEW4E0E25B643800
Name: v2_Prospective Data

Data Registry

You indicated that the study involves adding data to a registry or database for future use.

1 * What is the name of the registry/database to which data will be added? (If this study involves the VA, please state the name of the registry/repository and the CICERO protocol number it was approved under.)
Data will be stored in the Baltimore GRECC database GERI

2 * What is the purpose of the registry/database?
GERI is a secure password protected database behind the VA firewall for GRECC data.

3 * Who has oversight and controls access to the registry/database?
The GERI biostatistics core provides oversight and control over access to the database.

4 * Who will have access to the registry/database?
Study team members. If a team member leaves the study their access will be revoked immediately.

5 * How long will the data be stored in the registry/database?
Indefinitely as VA research data can not be destroyed. We will follow the VA RCS10.1 data retention/destruction policy.

6 * Are participants in the study allowed to request that their data be removed?
 Yes No

6.1 If No, explain why subjects will not be able to request that their data be removed:
VA research data can not be destroyed

ID: VIEW4EDE25BCFA400
Name: V2_Data Registry

Clinical Trial Registration

You indicated on the "Type of Research" page that your study is a clinical trial.

1 * Does the UM Clinical Trials Registry policy require registration of this trial?

Yes No

2 * Has this trial been registered?

Yes No

ID: VIEW4E093BF078C00
Name: v2_Clinical Trial Registration

Clinical Trial Registration Information

You indicated that this clinical trial has been registered.

1 * Was this trial registered at www.clinicaltrials.gov?
 Yes No

2 If no, was this trial registered on a site other than clinicaltrials.gov?
 Yes No

2.1 If Yes, specify the name of the other site:

2.2 Provide justification for registering this trial on this site:

3 * Registration Number
NCT02806336

ID: VIEW4E098BF1D0800
Name: v2_Clinical Trial Registration Information

Participant Selection

1 * How many local potential participants (or specimens/charts) do you anticipate will be screened for this study? **Screening includes determining potential participants' initial eligibility for and/or interest in a study.**
240

2 * How many participants (or specimens, or charts) will be enrolled/used for this study? **A local prospective participant is considered enrolled in the study when a UM-approved Informed Consent Document (not including separate screening consent forms) is signed.**

Local - the number being enrolled at this site:
240

Worldwide - the number being enrolled total at all sites (including local enrollment):
240

3 * Gender:

Male
 Female

4 * Age(s):

0 to 27 days (newborn infants)
 28 days to 12 months (Infant)
 13 months to 23 months (Toddler)
 2 to 5 years (Preschool)
 6 to 11 years (Child)
 12 to 17 (Adolescents)
 18 to 88 years (Adult)
 89 years and older

5 * Race/Ethnicity:

All Races Included
 American Indian or Alaskan Native
 Asian/Other Asian
 Asian/Vietnamese
 Black or African American
 Hispanic or Latino
 Mixed Race or Ethnicity
 Native Hawaiian or Pacific Islander
 White or Caucasian

6

* Language(s):

English
 Chinese
 French
 Italian
 Japanese
 Korean
 Local Dialect
 Spanish
 Vietnamese
 Other

6.1 Specify Other:**7***** Are you excluding a specific population, sub-group, or class?** Yes No**7.1****If Yes, indicate your justification for excluding a specific population, sub-group, class, etc.:***ID: VIEW4E0E519C1D000
Name: v2_Participant Selection*

Vulnerable Populations

1 * Will you be targeting ANY of the following Vulnerable Populations for enrollment? (Select all that apply)

- Employees or Lab Personnel
- Children (Minors)
- Cognitively Impaired/ Impaired Decision Making Capacity
- Pregnant Women/Fetuses
- Wards of the State
- Students
- Prisoners
- Nonviable Neonates or Neonates of Uncertain Viability
- Economically/Educationally Disadvantaged
- None of the above

Only select populations which you will be targeting for enrollment. Do not include populations that may be enrolled incidentally. Enrollment of a vulnerable population is considered to be "targeted" if the study team will be aware that a subject is from a vulnerable group as a result of interaction with the subject or collection of specific information about the subject, and the research team does not wish to exclude them. "Incidental" enrollment is limited to situations where a study team is unaware that a subject is from a vulnerable group.

ID: VIEW4E0E519917800
Name: v2_Vulnerable Populations

Eligibility

1 * Do you have an existing Eligibility checklist(s) for this study?

Yes No

1.1 If Yes, upload here. If you need a template, you can download it by clicking [HERE](#). The checklists you upload will also be available under the Documents tab of this application.

Name	Created	Modified Date
 Eligibility Checklist(0.01)	1/11/2017 3:25 PM	1/11/2017 3:25 PM

1.2 If No, create an eligibility checklist below:

List inclusion criteria (List each Inclusion Criteria individually, using the ADD button):

Number Criteria

View 1	BMI \geq 30 kg/m ²
View 2	Age \geq 60
View 3	Dysmobility as define by 1 or more of the following: Use of or prescribed an assistive walking device, measured gait speed $<$ 1.0 m/s, Four Square Step Test $>=$ 12 secs OR inability to complete the Four Square Step Test, and/or self-reported difficulty walking 1 km.
View 4	Community dwelling
View 5	Are a Veteran

List exclusion criteria (List each Exclusion Criteria individually, using the ADD button):

Number Criteria

View 1	Wheelchair or scooter dependent
View 2	Poorly controlled hypertension >180 systolic or >100 diastolic
View 3	Episode(s) of acute coronary syndrome, coronary revascularization, or major cardiac/vascular procedures within the prior 6 months
View 4	NYHA Class 3 or 4 heart failure
View 5	Symptomatic angina at rest or during exercise
View 6	Syncope within the past 12 months without known resolution or cause
View 7	Chronic lung disease requiring oxygen dependency
View 9	Severe spinal stenosis limiting ambulation
View 10	Known dementia
View 11	Mini Mental State Exam score $<$ 24
View 12	Transtibial or above the knee amputation
View 14	Poorly controlled diabetes as defined by HbA1C $>10\%$ or frequent hypoglycemic episodes
View 15	Currently undergoing chemotherapy and/or radiation therapy for cancer treatment
View 16	Other medical conditions or contraindications precluding patient participation in this study as per medical judgment of study team

After entering the inclusion and exclusion criteria above, click the Save link. CICERO will automatically generate a printable Eligibility Checklist for you to use in your research. To review the checklist, click on the resulting link below. This checklist is also available under the Documents tab of this application.

[Eligibility Checklist for HP-00069566_6 v3-21-2018-1521646040912\(0.01\)](#)

ID: VIEW4E0E5185F9000
Name: v2_Eligibility

Recruitment

1 * Describe plans for recruitment, including the identification of potential participants (or acquisition of charts/records/samples) and initial interactions with them: (If this study involves the VA please list all sites at which recruitment will take place.):
 Community dwelling obese Veterans (age >= 60) with mobility limitations will be recruited utilizing a variety of methods including the Baltimore GRECC subject recruitment registry, advertisements, referrals from VA providers in outpatient clinics, participants of MOVE and GeroFit, physical therapists, and community outreach. As the Covid-19 restrictions on face-to-face visit are lifted we anticipate that the number of GeroFit Veterans will return to the previous >100 subjects actively interacting with our staff, many of whom will qualify for this research program. There is a new GRECC falls and balance clinic and many of the older Veterans seen in this clinic would qualify for this study. Four to eight older Veterans are typically seen per week in this clinic. The providers in this clinic have agreed to refer potential subjects for this study.

The use of multiple recruitment strategies will allow us to maximize our outreach to a diverse pool of Veterans and to include those who do not routinely seek care at the VA. Interested individuals will initially undergo a telephone screen by the project coordinator or qualified research team member to assess eligibility for the study using our inclusion/exclusion criteria. Potential participants who pass the phone screen will be invited to our facility for further in-person screening to ensure that individuals are appropriate or safe to participate. The IRB and VA privacy officer grant a partial HIPAA waiver for the collection of protected health information during the recruitment and telephone screening phase of this study.

We would like to perform a computer-based screening using the VISN 5 Corporate Database Warehouse to screen for individuals who have had a previous fall, or use an assistive device and are at risk for falls. Also, we will use data pull with real Social Security Numbers (SSNs) from VA's Information and Computing Infrastructure (VINCI) to enhance recruitment goals within the VISN. This study already has an approved HIPAA Waiver and Consent Waiver for recruitment purposes. Potential subjects from the VISN will be mailed an IRB approved recruitment letter (uploaded in recruitment section), as well as an opt in/opt out post-card (uploaded in recruitment section). Postage will be provided on the opt in/out post-card, which will allow for potential subjects to indicate whether they would like to be contacted in the future related to the study. The opt in/out post-card will not list the subject's name, but rather will only provide a letter number that we will generate and store in a password protected file on the VA server prior to mailing the letter. If no response is received within two weeks, we will follow up with a phone call to gauge subject interest.

2 * Describe measures that will be implemented to avoid participant coercion or undue influence (if not applicable to the study, enter "N/A"):

Participants will be instructed to contact the research staff through a phone number listed on a brochure if they are interested in participation in this study. If the participant is a Veteran who receives care through the VAMHCS, they will be assured that their participation will not affect their medical care. To ensure continued consent and understanding of the study procedures, participants may, at any time point, ask to review individual specific study procedures and any pre-procedure preparation they will need to do. The participants will also be encouraged to take as much time as needed to decide whether they want to participate and will be encouraged to discuss the study with family and friends before signing the consent form.

3 * Who will recruit participants (or acquire charts/records/samples) for this study? (Check all that apply)

- PI
- Study Staff
- Third Party

3.1 If you are using a third party, specify Third Party Recruiters:

4 Upload any recruitment tools such as screening/telephone scripts and introductory letters (do not upload advertisements here):

Name	Created	Modified Date
 Opt In Out PostCard RISE 09242019.pub(0.02)	9/16/2019 3:48 PM	9/24/2019 10:32 AM
 VINCI RISE Recruitment Letter 09242019.doc(0.02)	9/16/2019 3:48 PM	9/24/2019 10:32 AM
 Invitation letter(0.04)	4/27/2016 9:31 AM	11/8/2018 12:58 PM
 Phone screen(0.01)	4/27/2016 9:16 AM	4/27/2016 9:16 AM

Advertising

1 * Will you be using advertisements to recruit potential participants?

Yes No

ID: VIEW4E0BCCF811000
Name: v2_Advertising

Advertising Detail

You indicated that you will be using advertisements to recruit potential participants.

1.1 *Select the mode(s) of advertising (check all that apply):

- Radio
- Internet
- Print
- Television
- Other

1.1.1 If Other, specify:

1.2 *Provide exact text of all proposed advertisement(s):

TEAR OFF NUMBER FLYER

DO YOU HAVE A SLOW WALKING SPEED?

DO YOU USE AN ASSISTIVE DEVICE TO WALK?

Participants are needed for a study to determine the impact of 3 months of exercise versus exercise and weight loss on fitness and body composition in patients who are overweight.

WHO MAY BE ELIGIBLE?

Men and women 60 years and older

Walk with a walking aid (cane or walker) OR have problems walking

Are a Veteran

Need to lose weight

For more information about this research study please contact: [contact] [name]

BROCHURE

MULTI-MODAL EXERCISE & WEIGHT LOSS IN OLDER VETERANS WITH LIMITED MOBILITY

An information guide for providers and potential study participants about this VA funded, IRB-approved study

University of Maryland School of Medicine

VA Maryland Health Care System

Geriatric Research, Education & Clinical Center

ABOUT THE STUDY

- About 1/3 of older Veterans are obese and obesity is a risk factor for mobility problems in older adults
- Using a walking aid can alter normal walking patterns and cause walking to be harder and more tiring, leading to mobility limitations
- Exercise training and weight loss may lead to improvements in mobility
- This study evaluates the impact of 3 months of exercise training & weight loss on fitness, functional performance, and body composition

WHO IS ELIGIBLE

- Are a Veteran
- Age 60 and older
- Walk with a walking aid (cane, walker) OR have difficulty walking around
- Need to lose weight ($BMI \geq 30 \text{ kg/m}^2$)
- Do not have a lower limb amputation

WHAT DO YOU HAVE TO DO?

- Medical history and physical exam
- Aerobic fitness assessments
- Strength and balance tests
- 24 hour food record
- Walking assessments
- Body composition scans (DEXA and CT scans)
- Questionnaires
- Follow up testing

RISKS

There are some risks of chest pain and musculoskeletal pain with exercise. You will be assessed at the start of the study to make sure it is safe for you to begin an exercise training program

If you think you might be interested in this study, please contact the Geriatric Research, Education & Clinical Center at

[contact] [name]

Providers can call the same number above with the name(s) of persons who may be interested in enrolling in the study.

RECRUITING POSTER

Do you have a slow walking speed?

Do you use an assistive device to walk?

If so, you may be eligible for a 3 month research study investigating the effect of exercise training & weight loss on fitness and body composition in older adults

You may qualify if you:

- Are a Veteran
- Use a cane or walker OR have problems walking
- Are 60 years or older
- Need to lose weight ($BMI \geq 30 \text{ kg/m}^2$)

If you are interested in more information, please call [contact] [name]

1.3 *Upload advertisement(s) here:

Name

-  Tear off number flyer 2.27.21(0.07)
-  Recruiting Poster 2.27.21(0.07)
-  Brochure 2.27.21(0.08)

Created

- 4/27/2016 9:38 AM
- 4/27/2016 9:57 AM
- 4/27/2016 9:52 AM

Modified Date

- 3/10/2021 10:49 AM
- 3/10/2021 10:34 AM
- 3/10/2021 10:31 AM

ID: VIEW4E0BCE82B8C00
Name: v2_Advertising Detail

Research Related Risks

If you uploaded a separate research protocol document in the 'Research Protocol' page, cite the applicable section and page numbers from that document in the answer box below.

1 * Individually list each research-related risk, using a separate line for each. Next to each risk, delineate the likelihood/seriousness of the risk, and the provisions for minimizing the risk:

There are potential risks associated with some of the procedures included in this study. However, the procedures have been planned by the investigators to minimize the danger of any major complication. All subjects will undergo a thorough medical and history examination at entry into the study to assure that it is safe for them to participate in the study. All study procedures will be supervised by qualified personnel who will carefully monitor the participants.

